Participants randomized to the precision evaluation arm and determined to be at low risk will be treated for symptoms and risk factor management according to current guideline recommendations. While it is expected that this will resolve symptoms in nearly all cases it is recognized that chest pain will persist in some despite medical treatment. In some cases, additional non-cardiac diagnostic testing may be pursued. In other cases, the site clinician may decide that further cardiac testing is warranted, in which case a cCTA followed by selective FFR_{CT} should be performed. Details regarding such decision making will be captured in the case report form.

V. STUDY PROCEDURES

V.A. Patient Screening for Eligibility

Patients will be screened by site personnel for eligibility and provided information about the study. Patients' not meeting inclusion and or having exclusion criteria will be documented as being excluded. Patients meeting inclusion and not meeting any exclusion criteria will be provided an informed consent form to review and sign prior to being randomized into the study.

Inclusion Criteria

1. Age ≥ 18 years
2. Stable typical or atypical symptoms suggesting possible significant coronary artery disease (CAD) with further non-emergent testing or elective catheterization recommended to evaluate the presence of suspected significant CAD. Stable chest pain (or equivalent) includes those who have fully been ruled out for Acute Coronary Syndrome (ACS) and for whom elective testing is recommended, regardless of the venue in which they are seen.
3. If prior CV testing has occurred, it must have been performed greater than one year prior to randomization, and the following must be met:
 - a) cCTA or invasive coronary angiography (ICA) with stenosis $< 50\%$
 - b) Quantified coronary artery calcium (CAC) < 100 AG
4. Safe performance of cCTA:
 - a) Creatinine clearance ≥ 45 ml/min per most recent measurement within 90 days
 - b) For a female participant of childbearing potential (those who have not been surgically sterilized or are not postmenopausal), a pregnancy test must be performed with negative results known within 7 days prior to randomization
5. Willingness to comply with all aspects of the protocol, including adherence to the assigned strategy and follow-up visits regardless of actual testing performed
6. Ability to provide written informed consent

Exclusion Criteria

1. Acute chest pain (in patients who have not been ruled out for ACS)

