In accordance with the Declaration of Helsinki, each participant is free to withdraw from the study at any time. Investigator(s) also have the right to withdraw participants from the study in the event of illness or other reasons concerning the health or wellbeing of the participant, or in the case of lack of cooperation. Should a participant decide to withdraw or should the investigator(s) decide to withdraw the participant, all efforts will be made to complete and report the observations up to the time of withdrawal as thoroughly as possible. If possible, a complete final evaluation at the time of the participant's withdrawal should be made. The reason for withdrawal must be noted in the eCRFs.

V.G. Schedule of Assessments

	Screening	Randomization Day 1	Day 45 (+/- 14 d)	6-mo. (+/- 30d)	12-mo. (+/- 30d)
Informed consent	X				
Medical history	X				
Cardiovascular update ¹			X	X	X
Concomitant cardiovascular medications	X		X	X	X
Cardiovascular risk factors (including PROMISE minimal risk score data entry for randomization)	X				
² Pregnancy test	X				
³ Creatinine	X				
⁴ Resting 12-lead ECG	X				
QoL evaluation: SAQ, EQ5D-5L	X		X	X	X
Participant Satisfaction Questionnaire			X		
Randomization		X			
Initial diagnostic invasive or noninvasive test performed (if assigned)		Prior to 45 day visit			
Cardiac imaging/testing clinical report and image collection			X	X	X
Interval assessment for CV events and testing			X	X	X
Endpoint assessments			X	X	X

1. During cardiovascular update, if participants have received an additional diagnostic test, a cardiovascular procedure or have been hospitalized since the last visit, additional data will be collected
2. For a female participant of childbearing potential, a pregnancy test must be performed with negative results known within 7 days prior to randomization
3. Creatinine blood draw required only for participants without a recent normal value (most recent within previous 90 days)
4. Resting 12-lead ECG preferred in last 30 days (optional, clinical care only)

VI. ADDITIONAL ASSESSMENTS AND SUBSTUDIES

VI.A. Quality of Life Assessments

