The primary endpoint of this study is based on time-to-first occurrence of any of the components, which is defined as a composite of MACE (all-cause death, non-fatal MI) or invasive cardiac catheterization without obstructive CAD (obstructive CAD defied as diameter stenosis $\geq 50\%$, $FFR \leq 0.80$, or $iFR \leq 0.89$) over 12-month follow-up. The time from randomization to the first event among the components of the primary endpoint will be measured (in days) for those who experienced an event and calculated as the date of the first event minus the date of randomization. For participants who do not experience any of the primary endpoint component events or who withdraw consent or drop out of the study before experiencing an event, time from randomization to the date of last contact will be used in the analysis, and those participants will be considered as censored observations in the time-to-event analysis.

The primary and secondary endpoint comparisons between the randomized groups in this study will be performed according to the principle of "intention-to-treat" (ITT); that is, participants will be analyzed according to the treatment arm to which they were randomized, regardless of subsequent crossover or post-randomization strategy.

The log-rank test⁵³ will be the primary analytic tool for statistically assessing outcome differences between the two randomized treatment strategies with respect to the primary composite endpoint. Cox proportional hazards model⁵⁴ will be used to estimate the hazard ratio (HR) and 95% confidence interval (CI) summarizing the difference in outcome between the two randomized arms, using treatment as the only predictor in the model. Proportionality assumption in the Cox model (i.e., constant hazard over time) will be checked and tested.

Cumulative event rates will be calculated according to the method of Kaplan and Meier⁵⁵ for each randomized arm as a function of time from randomization, and the estimated event probabilities

will be displayed graphically. Adjusted HR and its 95% CI will be estimated using Cox proportional hazards model by including pre-specified baseline risk factors as covariates in the model.

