9.2 Primary Efficacy Analysis

The primary endpoint of this study is estimated as time to first occurrence of any of its three following components:

- All-cause death
- Non-fatal MI
- Invasive cardiac catheterization without obstructive CAD

Each death will be adjudicated for cause and date by the CEC. Potential MI cases will be adjudicated for MI yes/no, fatal/non-fatal, MI type, and date of MI by the CEC. Cath without obstructive CAD is the absence of obstructive CAD, defined as diameter stenosis $\geq 50\%$ in a vessel ≥ 2 mm both assessed by QCA (or site read if QCA is not available), $FFR \leq 0.80$, or $iFR \leq 0.89$. The catheterization component of the primary endpoint will be determined according to the algorithm diagrammed below:

To derive the catheterization component of the primary endpoint, site, core lab and DCRI entered clinical data present in the clinical EDC will be extracted and processed through a HeartFlow Cath Algorithm to be classified as Obstructive CAD, No Obstructive CAD, Indeterminate, or Incomplete data. Each ICA classified as either Obstructive CAD, No Obstructive CAD, or Indeterminate will undergo individual Medical Monitor review. For ICAs receiving a final classification as confirmed Obstructive CAD or No Obstructive CAD, the results are considered final. For ICAs confirmed by the Medical Monitor as Indeterminate or ambiguous, CEC adjudication will make the final determination. Incomplete ICAs will be reprocessed through the Cath Algorithm once data are complete and query free.

The time from randomization to the first event among the components of the primary endpoint will be measured (in days) for those who experienced an event and calculated as the date of the first event minus the date of randomization + 1. For participants who do not experience any of the primary component events or who withdraw consent or drop out of the study before experiencing an event, time from randomization to the date of last contact + 1 will be used in the analysis, and those participants will be considered as censored observations in the time-to-event analysis. The 12-month analysis will be censored at 395 days (365 days + 30 day visit window) such that only events on or before this time will be counted in the analysis and event free participants with follow-up greater than 395 will be set to 395.

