The primary and major secondary endpoint comparisons between the randomized groups in this study will be performed according to the principle of intention-to-treat; that is, participants will be analyzed according to the treatment (evaluation) arm to which they were randomized, regardless of subsequent crossover or post-randomization strategy.

The log-rank a non-parametric test will be the primary statistical methodology to test for outcome differences between precision care arm and usual care arm with respect to the primary composite endpoint. The Cox proportional hazards model will be used to estimate the average treatment effect size using the hazard ratio (HR) and 95% confidence interval (CI) with treatment assignment as the only covariate in the model. The proportionality assumption (constant hazard over time) in the Cox model will be assessed using the cumulative sums of martingale residuals and the Kolmogorov-type Supremum test. Although log-rank statistic (primary method) is robust under non-proportional hazards it's not optimal due to loss of some statistical power. Thus, if the proportional hazards assumption is violated a two-stage procedure will be implemented (Qiu and Sheng 2008). Due to interim analysis conducted by the DSMB, the final analysis type I error rate (α) will be adjusted as $0.05 - \alpha$ spent at any interim analyses. Cumulative event rates will be calculated according to the method of Kaplan-Meier for each randomized arm as a function of time (in days) from randomization to the time of event or censoring + 1, and the estimated event probabilities will be displayed graphically.

As a supportive analysis, adjusted HRs and 95% CIs will be estimated using the Cox proportional hazards model by including pre-specified baseline risk factors as covariates in the model. These covariates will include: age, sex, CAD equivalent (diabetes, history of peripheral artery disease, or cerebrovascular), and intended first test strata: invasive/non-invasive.

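### Protocol V.F lets site staff who know the arm end a participant's follow-up for illness or undefined non-cooperation; with censoring at last contact, this permits informative censoring that no planned analysis tests

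*Protocol*

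**What the plan says.** **Withdrawal.** Protocol V.F (Participant Withdrawal) covers both the participant's own decision and the investigator's. On the second: "Investigator(s) also have the right to withdraw participants from the study in the event of illness or other reasons concerning the health or wellbeing". The same sentence adds a ground unrelated to health: "or in the case of lack of cooperation". The object is the study, not the assigned evaluation strategy. None of the grounds has criteria.

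**Data afterwards.** V.F says that "all efforts will be made to complete and report the observations up to the time of withdrawal as thoroughly as possible". It adds a final evaluation if possible and an eCRF entry giving the reason. It describes no later event collection, record review or vital-status check.

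**Primary analysis.** Protocol VIII.B states that for those who "drop out of the study before experiencing an event, time from randomization to the date of last contact will be used in the analysis". SAP 9.2 repeats the rule and adds that "those participants will be considered as censored observations in the time-to-event analysis". Neither names withdrawal by the investigator; it falls under dropping out only by inference.

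**Related text.** Inclusion criterion 5 in protocol V.A asks for willingness at entry, including "adherence to the assigned strategy and follow-up visits regardless of actual testing performed". On intention to treat, SAP 9.2 says "participants will be analyzed according to the treatment (evaluation) arm to which they were randomized, regardless of subsequent crossover or post-randomization strategy". The sensitivity analyses in SAP 9.3.4 cover the risk-score cut point, the risk groups and COVID-19. Multiple imputation of missing follow-up appears only under the win ratio in SAP 9.3.1.

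**The concern.** The log-rank test, the Cox model and the Kaplan-Meier estimates all assume that censoring is unrelated to the risk of the event. Withdrawal for illness is hard to reconcile with that assumption when the endpoint is death, MI or catheterization without obstructive disease.

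The decision rests with site staff who deliver the assigned strategy and so know the arm. Only endpoint adjudication is described as blinded (protocol VII.D). The label open-label is not used in the documents; it is inferred from the design.

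Ending follow-up also seems unnecessary here. Protocol IX.A already lets clinicians take another diagnostic pathway as a documented deviation, and SAP 5.2 handles non-adherence through a per-protocol population. If withdrawals track prognosis and differ between arms, the primary hazard ratio is biased, and nothing in the plan would show it.

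**Working it through.** **Inputs** (protocol VIII.A, SAP 7): 1050 per arm; 8% vs 5% primary event rate at 1 year; 10% attrition; two-sided alpha 0.05; log-rank test.

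**1. The plan's own figure.** Exponential hazards are -ln(0.92) and -ln(0.95), so HR = 0.0513/0.0834 = 0.615. Freedman's formula for 90% power gives (1.960 + 1.282)² × (1.615/0.385)², or 186 events after rounding up. With 12-month uniform accrual, at least 12 months of follow-up and 10% per year exponential loss, this needs 2105 participants, against 2096 stated. The figure reproduces to within 3%.

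**2. Scale.**
- Attrition allowance: 0.10 × 1050 = 105 per arm.
- Would-be events at 8%: 0.08 × 1050 = 84 in an arm.
- If the 105 dropouts had average risk, they would hold at most 105 × 0.08 = 8.4 would-be events.

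**3. Simulation.** Assumptions: 1050 per arm, 12 months of follow-up for all, 10% non-informative attrition, and in addition a share f of would-be events censored at the event time. There were 4000 replicates, so the 95% Monte Carlo margin is about ±0.7 points near 5% and ±1.6 points near 50%.

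| True rates (usual vs precision) | Would-be events lost | Two-sided rejection | Mean HR |
|---|---|---|---|
| 8% vs 8% | none | 4.7% | 1.00 |
| 8% vs 8% | 5%, precision only | 5.6% | 0.95 |
| 8% vs 8% | 10%, precision only | 10% | 0.90 |
| 8% vs 8% | 20%, precision only | 27% | 0.80 |
| 8% vs 8% | 30%, precision only | 54% | 0.70 |
| 8% vs 5% | none | 78% | 0.61 |
| 8% vs 5% | 5%, usual care only | 68% | 0.65 |
| 8% vs 5% | 10%, usual care only | 54% | 0.68 |
| 8% vs 5% | 20%, usual care only | 29% | 0.77 |
| 8% vs 5% | 10%, both arms | 74% | 0.61 |
| 8% vs 5% | 20%, both arms | 67% | 0.61 |

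The baseline here is 78%, not 90%, because follow-up stops at 12 months for everyone and gives about 130 events. The plan's 90% reproduces only when events beyond 12 months are counted. That is a separate matter; only the changes within the table bear on this point.

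**4. Hand check of one row.** Losing a share f of events in one arm multiplies its hazard by about 1 - f. For f = 0.10 and 151 events, the expected z is |ln 0.90| × √151/2 = 0.105 × 6.14 = 0.65. Rejection is Φ(0.65 - 1.96) + Φ(-0.65 - 1.96) = 0.095 + 0.005 = 10%, as simulated.

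**5. The extreme case.** With true counts of 84 vs 84, hiding 23 events in one arm gives 84 vs 61. The pooled rate is 145/2100 = 0.0690, the standard error is √(0.0690 × 0.9310 × 2/1050) = 0.01107, and z = (23/1050)/0.01107 = 1.98, p = 0.048. Twenty-three is 2.2% of the arm, but 23/84 = 27% of its events and 23/8.4 = 2.7 times what average-risk dropout could contain.

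**The case against.** The case against is strong on direction and size, less so on the rule itself.

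- **Bias towards precision.** A reader might infer that the clause favours the sponsor's strategy, because a low-risk precision participant who insists on testing could be called uncooperative and withdrawn. The documents do not support this. Such a participant has a route within the trial: the synopsis and protocol IV.G, V.C and V.E provide for cCTA, IX.A treats other pathways as documented deviations, and SAP 5.2 still counts a low-risk participant whose first test is CTA as per-protocol. Leaving the strategy is not a listed reason for withdrawal. Usual-care participants can also be uncooperative: they may decline testing, which SAP 5.2 anticipates in either arm, or seek cCTA within the barred 45 days.
- **Contradiction.** A reader might see V.F as contradicting criterion 5 and the intention-to-treat rule. Strictly it does not. The first is willingness at entry, and the second says which arm a participant is counted in, not how long follow-up lasts. Both do show an intention to keep off-strategy participants.
- **A reversed result.** Hiding 23 events requires every such withdrawal to be a would-be event, all in one arm. Low-risk precision participants alone could not supply them: 20% of 1050 is 210, and 210 × 8% = 17 events even at the full rate. At 5% lost, the error rate moves only from 4.7% to 5.6%.
- **Removal.** Participants are censored, not deleted; earlier time and events count. V.F does not forbid later collection, and the consent pages and eCRF are not in the copy reviewed.
- **Existing safeguards.** Adjudication is blinded, the withdrawal reason is recorded, US follow-up is central unless the site disallows it, and SAP 10 tabulates disposition and follow-up visits by arm.
- **Burden.** Contacts can weigh on a seriously ill participant.

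These points remove any claim about direction or likely size. They leave a stated permission to end follow-up on grounds related to prognosis, with no analysis that would reveal the effect.

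**Conclusion.** The point holds as a weakness in a stated rule. Followed as written, V.F with SAP 9.2 permits informative censoring of the primary comparison by staff who know the arm, and no planned sensitivity analysis addresses it.

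Its size is unknown, because no document gives an expected number of investigator withdrawals. The simulations show sensitivity, not a forecast: about 8 would-be events lost in the precision arm only (10% of 84) would roughly double the type I error rate; the same share lost in usual care only would cut simulated power from 78% to 54%; equal loss costs some power but leaves the hazard ratio at about 0.61.

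The conclusion assumes that investigator withdrawal is handled as dropout, that follow-up ends with it, and that illness predicts the endpoint. It does not support a statement that the trial is biased towards either arm. It is a worthwhile, inexpensive improvement.

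**What to change.** 1. **Protocol V.F and eCRF.** Record separately that the assigned strategy was stopped and that consent for follow-up was withdrawn. Record illness, a change of diagnostic pathway or non-cooperation with testing as a deviation. Continue event, catheterization and vital-status collection at the existing 45-day, 6-month and 12-month contacts unless the participant withdraws consent for follow-up.
2. **SAP 9.2.** Censor early only for withdrawn consent for follow-up or loss to follow-up, and report early censoring by arm and reason. A sensitivity analysis of the primary endpoint for informative censoring would cover whatever early censoring remains.

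This changes data collection only; clinical decisions stay with the care team. The cost is protocol and eCRF wording and some additional follow-up contacts, made through the call center and site coordinators already in place.

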V. STUDY PROCEDURES V.D. Participant Follow-Up (24M)	NA	Collection of the following: 
 • Any cardiovascular test – both written report and test output • Any cardiovascular imaging – both written report and image file
V.I. ADDITIONAL ASSESSMENTS AND SUBSTUDIES V.I.A. Quality of Life Assessments	Quality of life (QoL) assessments will be conducted at baseline, 45 days, 6 months and 12 months.	Quality of life (QoL) assessments will be conducted at baseline, 45 days, 6 months, 12 months, and 24 months.
VIII.B. Statistical Analysis Plan C) Cost Sensitivity Analyses	In secondary sensitivity analyses, we will apply US unit costs to all resource use of all patients and compare costs between treatment groups across all patients enrolled in the trial.	In secondary sensitivity analyses, we will compare resource use and costs between treatment groups in the US.
XII. REFERENCES	References listed	References updated via EndNote

Amendment from version 1.1 dated July 31, 2018 to version 1.2 dated September 10, 2018

Section	Version 1.1	Version 1.2
Table of Contents	V.E. Cross Over Participants	V.E. Testing in precision evaluation arm for participants assigned to no immediate testing
I. Study Synopsis – Study Design and Methods	
All subsequent decisions in the usual care arm regarding additional testing, medications, and/or procedures will be at the discretion of the responsible clinical care team; the use of cCTA as the initial diagnostic strategy is not allowed in the usual care arm.
 
Usual Care: For participants randomized to usual care, the participant's care team will select the specific noninvasive stress test (exercise electrocardiogram, stress nuclear imaging [including PET], stress MR, or stress echocardiogram); OR invasive test: (direct to diagnostic catheterization). The use of cCTA as the initial diagnostic strategy is explicitly excluded in this arm.
	
All subsequent decisions in the usual care arm regarding additional testing, medications, and/or procedures will be at the discretion of the responsible clinical care team; the use of cCTA as the initial diagnostic strategy is not allowed in the usual care arm and prohibited as a subsequent test for the first 45 days after randomization.
 
Usual Care: For participants randomized to usual care, the participant's care team will select the specific noninvasive stress test (exercise electrocardiogram, stress nuclear imaging [including PET], stress MR, or stress echocardiogram); OR invasive test: (direct to diagnostic catheterization). The use of cCTA as the initial diagnostic strategy is explicitly excluded in this arm and prohibited as a subsequent test for the first 45 days after randomization.

I. Study Synopsis - Sample Size Considerations	
Assumed rates are based on 30% assigned to guideline- recommended care with symptom management and no planned testing (within which 30% will cross over to cCTA with selective FFR_{CT}); and overall 10% will not receive assigned testing; enrolling 1050 participants per group (2100 total participants) would provide at least 90% power to demonstrate superiority accounting for 10% attrition rate.
	
Assumed rates are based on 20% assigned to guideline- recommended care with symptom management and no planned testing (within which 30% will cross over to cCTA with selective FFR_{CT}); and overall 10% will not receive assigned testing; enrolling 1050 participants per group (2100 total participants) would provide at least 90% power to demonstrate superiority accounting for 10% attrition rate.

III.A. Prior Literature and Studies – Rationale and Evidence for Incorporation of a Strategy of Guideline-Recommended Care without Planned Testing in Low Risk patients	The Risk Tool developed using the PROMISE cohort employs 10 readily available clinical variables and has been validated in the SCOT-HEART population ^{33, 34}	The Risk Tool developed using the PROMISE cohort employs 10 readily available clinical variables (such as tobacco usage, ethnicity/race, and age) and has been validated in the SCOT-HEART population ^{33, 34}
IV.E. Rationale for Selection of Testing in Each Arm – Usual Care Arm	The use of cCTA is explicitly excluded as the initial diagnostic strategy in this arm.	The use of cCTA is explicitly excluded as the initial diagnostic strategy in this arm and prohibited as a subsequent test for the first 45 days after randomization.
IV.F. Randomization Method	Risk will be classified by a risk tool using pre-test clinical characteristics derived in the PROMISE trial and validated in SCOT-HEART.	Risk will be classified by a risk tool using pre-test clinical characteristics (including tobacco usage, ethnicity/race, and age) derived in the PROMISE trial and validated in SCOT-HEART.
IV.F. Randomization Method	The use of cCTA is explicitly excluded as the initial diagnostic strategy in this arm.	The use of cCTA is explicitly excluded as the initial diagnostic strategy in this arm and prohibited as a subsequent test for the first 45 days after randomization.
V.C. Participant Cohort Assignment – Usual Care Arm	Performance of cCTA as the initial test is excluded in this arm.	Performance of cCTA as the initial test is excluded in this arm and prohibited as a subsequent test for the first 45 days after randomization.
V.E Cross over in precision evaluation arm participants	Section title: Cross over in precision evaluation arm participants Previous text deleted and replaced	Section title: Testing in precision evaluation arm for participants assigned to no immediate testing New text

VIII.A. Sample Size Determination and Statistical Power	Assuming 10% of usual care participants will receive angiography as a first test results in an 8% primary endpoint event rate at 1 year in the usual care group and 5% (absolute) event rate in the precision care group (i.e., 37.5% relative effect size) with 30% assigned to guideline-recommended care with symptom management and no planned testing.	Assuming 10% of usual care participants will receive angiography as a first test results in an 8% primary endpoint event rate at 1 year in the usual care group and 5% (absolute) event rate in the precision care group (i.e., 37.5% relative effect size) with 20% assigned to guideline-recommended care with symptom management and no planned testing.
---	---	---

Amendment from version 1.2 dated September 10, 2018 to version 1.3 dated November 21, 2018

Section	Version 1.2	Version 1.3
Throughout protocol	Non hyperemic pressure ratio (NHPR) ... NHPR... NHPR <0.90	Instantaneous wave free ratio (iFR) ... iFR... iFR ≤0.89
I. Study Synopsis – Primary Endpoint	Time to a composite of: MACE (all cause death, non-fatal MI) or invasive cardiac catheterization without obstructive CAD (obstructive CAD defined as diameter stenosis ≥50% according to clinical site interpretation, FFR≤0.80, or NHPR<0.90) at one year (intention to treat)	Time to a composite of: MACE (all cause death, non-fatal MI) or invasive cardiac catheterization without obstructive CAD (obstructive CAD defined as diameter stenosis ≥50% according to core-lab adjudicated quantitative coronary analysis (QCA), FFR≤0.80, or iFR≤0.89) at one year (intention to treat)
I. Study Synopsis – Inclusion Criteria	Stable typical or atypical symptoms suspicious for coronary artery disease with further non-emergent testing or elective catheterization recommended to evaluate the presence of suspected coronary artery disease Safe performance of cCTA: Creatinine clearance ≥45 ml/min For a female participant of childbearing potential, a pregnancy test must be performed with negative results known within 7 days prior to randomization	Stable typical or atypical symptoms suggesting possible coronary artery disease (CAD) with further non-emergent testing or elective catheterization recommended to evaluate the presence of suspected CAD. Stable chest pain includes those who have fully been ruled out for Acute Coronary Syndrome (ACS) and for whom elective testing is recommended, regardless of the venue in which they are seen. Safe performance of cCTA: Creatinine clearance ≥45 ml/min per most recent measurement within 90 days For a female participant of childbearing potential (those who have not been surgically sterilized or are not postmenopausal), a pregnancy test

		must be performed with negative results known within 7 days prior to randomization
I. Study Synopsis – Exclusion Criteria	
3. Noninvasive or invasive CV testing for CAD within 1 year
 
4. Lifetime history of any obstructive CAD (no prior CABG or PCI, stenosis $\geq 50\%$) or known EF $\leq 40\%$ or moderate to severe valvular or congenital cardiac
 
5. Contraindications to cCTA including but not limited to estimated creatinine clearance (GFR) < 45 ml/min measured within 90 days.
 
6. Exceeds local weight or size limit for cCTA or cardiac catheterization
	
3. Noninvasive or invasive CV testing within 1 year (for suspected CAD). CV testing for CAD refers to any stress tests, ICA and cCTA (including calcium scoring) only. Resting ECG and resting echocardiogram are not exclusionary.
 
4. Lifetime history of known obstructive CAD (prior myocardial infarction, CABG or PCI, stenosis $\geq 50\%$), known EF $\leq 40\%$ or other moderate to severe valvular or congenital cardiac disease.
 
5. Contraindications to cCTA including but not limited to creatinine clearance (GFR) < 45 ml/min as per most recent measurement taken within 90 days.
 
6. Exceeds the site's weight or size limit for cCTA or cardiac catheterization

IV.B. Primary Objective and Endpoints	The primary endpoint is a composite of: MACE (all cause death and non-fatal MI) or invasive cardiac catheterization without CAD (no coronary stenosis $\geq 50\%$, or with FFR ≤ 0.80 , or non-hyperemic pressure ratio (NHPR) < 0.90). The primary study hypothesis will be tested at one year using an intention to treat analysis	The primary endpoint is a composite of: MACE (all cause death and non-fatal MI) or invasive cardiac catheterization without CAD (no coronary stenosis $\geq 50\%$ according to QCA by core-lab adjudication, or with FFR ≤ 0.80 , or instantaneous wave free ratio (iFR) ≤ 0.89). The primary study hypothesis will be tested at one year using an intention to treat analysis
IV.G. Diagnostic Evaluations and Subsequent Care – Description of Evaluations to be performed	A pregnancy test will be required for female participants of childbearing potential, and a creatinine blood test will be required for participants without a recent normal value (within previous 90 days).	A pregnancy test will be required for female participants of childbearing potential (those who have not been surgically sterilized or are not postmenopausal), and a creatinine blood test will be required for participants without a recent normal value (most recent measurement taken within previous 90 days).

IV.G. Diagnostic Evaluations and Subsequent Care – Subsequent Care		
Added text:
 
For patients in the Precision Evaluation Arm, ICA cannot be performed unless one of the following criteria are met:
 
 • Any stenosis $\geq 90\%$ identified by cCTA • Left Main stenosis $\geq 30\%$ identified by cCTA • Plaque rupture identified by cCTA • Lesion-specific FFR_{CT} ≤ 0.85 in vessels with reference vessel size 2.0mm or greater in diameter
V.A. Patient Screening for Eligibility – Screening visit (in-person)	
At the screening visit, patients will undergo the following:
 
...
 
Pregnancy test (for females of child-bearing potential)
 
...
	
At the screening visit, patients will undergo the following:
 
...
 
Pregnancy test (for females of child-bearing potential – those who have not been surgically sterilized or are not postmenopausal)
 
...

V.A. Patient Screening for Eligibility – Inclusion Criteria	
2. Stable typical or atypical symptoms suggesting possible coronary artery disease (CAD) with further non-emergent testing or elective catheterization recommended to evaluate the presence of suspected CAD.
 
3. Safe performance of cCTA:
 
 Creatinine clearance ≥ 45 ml/min For a female participant of childbearing potential, a pregnancy test must be performed with negative results known within 7 days prior to randomization 	
2. Stable typical or atypical symptoms suggesting possible coronary artery disease (CAD) with further non-emergent testing or elective catheterization recommended to evaluate the presence of suspected CAD. Stable chest pain includes those who have fully been ruled out for Acute Coronary Syndrome (ACS) and for whom elective testing is recommended, regardless of the venue in which they are seen.
 
3. Safe performance of cCTA:
 
 Creatinine clearance ≥ 45 ml/min per most recent measurement within 90 days

[figure not shown]
		
b. For a female participant of childbearing potential (those who have not been surgically sterilized or are not postmenopausal), a pregnancy test must be performed with negative results known within 7 days prior to randomization

V.A. Patient Screening for Eligibility – Exclusion Criteria	
 1. Acute chest pain 2. Unstable clinical status 3. Noninvasive CV testing within 1 year (for suspected CAD), including coronary artery calcium score 4. History of known obstructive CAD (prior myocardial infarction, CABG or PCI, stenosis $\geq 50\%$), known EF$\leq 40\%$ or other moderate to severe valvular or congenital disease 5. Contraindications to cCTA including but not limited to estimated creatinine clearance (GFR) <45 ml/min 6. Any condition leading to possible inability to comply with the protocol 7. Exceeds the weight or size limit for cCTA or cardiac catheterization at the site 8. Life expectancy less than 2 years due to non-cardiovascular comorbidities 9. Enrolled in an investigational trial that involves a non-approved cardiac drug or device which has not reached its primary endpoint 10. Any condition that might interfere with the study procedures or follow-up 	
 1. Acute chest pain 2. Unstable clinical status 3. Noninvasive or invasive CV testing within 1 year for suspected CAD, CV testing refers to stress tests, ICA, and cCTA (including coronary artery calcium score) only. Resting ECG and resting echocardiogram are not exclusionary. 4. Lifetime history of known obstructive CAD (prior myocardial infarction, CABG or PCI, coronary artery stenosis $\geq 50\%$), known EF$\leq 40\%$ or other moderate to severe valvular or congenital cardiac disease 5. Contraindications to cCTA including but not limited to creatinine clearance (GFR) <45 ml/min as per most recent measurement taken within 90 days 6. Exceeds the site's weight or size limit for cCTA or cardiac catheterization 7. Any condition leading to possible inability to comply with the protocol procedures and follow-up 8. Any condition that might interfere with the study procedures or follow-up 9. Enrolled in an investigational trial that involves a non-approved cardiac drug or device which has not reached its primary endpoint 10. Life expectancy less than 2 years due to non-cardiovascular

		comorbidities
VII.A. Primary Endpoint Definitions – Cardiac catheterization without obstructive coronary artery disease (diameter stenosis <50%, any FFR >0.80 or NHPR ≥0.90)	Cardiac catheterization without obstructive coronary artery disease will be defined as the absence of any $\geq 50\%$ stenosis or hemodynamic indication of significance in any major epicardial vessel including side branches ≥ 2 mm in diameter, as determined by the clinical site interpretation.	Cardiac catheterization without obstructive coronary artery disease will be defined as the absence of any $\geq 50\%$ stenosis or hemodynamic indication of significance in any major epicardial vessel, including side branches, ≥ 2 mm in diameter, as determined by core-lab adjudicated QCA or invasive FFR or iFR.
II.B. Secondary Endpoint Definitions	Myocardial infarction Myocardial infarction will be characterized according to Universal MI definition subtypes as Type 1, 2, 3, 4a, 4b, 4c, and 5.	Myocardial infarction Myocardial infarction will be characterized according to the 4 th Universal MI definition for Spontaneous MI and the SCAI definition for periprocedural MIs.

Amendment from version 1.3 dated November 21, 2018 to version 1.4 dated February 1, 2019

Section	Version 1.3	Version 1.4
VII.A. Primary Endpoint Definitions – Myocardial infarction	
Acute myocardial infarction (MI) is defined as having evidence of myocardial necrosis in a clinical setting consistent with myocardial ischemia⁵¹. Specifically, MI is defined as having:
 
1) Typical rise and/or gradual fall in cardiac biomarker level (cardiac troponin preferred) with values exceeding the 99th percentile of the institutional upper limit of normal (ULN) (generally 2x the ULN)
 
AND either:
 
2) Clinical presentation defined as typical cardiac ischemic type pain/discomfort or dyspnea felt to be due to ischemia and consistent with the diagnosis of myocardial ischemia and infarction
	
Acute myocardial infarction (MI) is defined as having evidence of myocardial necrosis in a clinical setting consistent with myocardial ischemia. Specifically, the Fourth Universal Definition⁵¹ of type I MI is defined as:
 
Detection of a rise and/or fall of cTn values with at least 1 value above the 99th percentile URL and with at least 1 of the following:
 
 • Symptoms of acute myocardial ischemia; • New ischemic ECG changes; • Development of pathological Q waves; • Imaging evidence of new loss of viable myocardium or new regional wall motion abnormality in a pattern consistent with an ischemic etiology; • Identification of a coronary thrombus by angiography

[figure not shown]
[figure not shown]
